The 6 month follow up has been completed for this study and preliminary results indicate that eHealth Familias Unidas in schools has high family engagement (mean number of sessions = 8.4 out of 12;  $SD = 4.6$ ) and is having a significant effect on parent-adolescent communication ( $b = -5.11$ ;  $p = .05$ ; see Figure below), the intervention’s mediator. Results on drug use and unsafe sexual behavior are in the expected direction and of similar effect size as in previous Familias Unidas trials (effect sizes = 0.79 and 0.40 for drug use and unsafe sex, respectively) at 6 month follow up. It is worth noting that in all of our intervention trials, changes in parent-adolescent communication were observed between the baseline and 6-month follow up assessment, and those changes in turn significantly impacted the distal outcomes, drug use and unsafe sex, at subsequent time points.

Pilot Study of eHealth Familias Unidas in Primary Care. [name] and colleagues evaluated the feasibility and acceptability of delivering eHealth Familias Unidas

Primary Care in a universal sample of Hispanic youth. Study staff recruited 48 Hispanic youth and their primary caregivers from four sites: a mobile clinic, an academic pediatric clinic, a public health clinic (Jackson Memorial Hospital), and a private practice clinic (Kidstown Pediatrics, LLC). The pilot study's aim was not to assess efficacy or effectiveness but rather to assess the: 1) feasibility of recruiting families from pediatric care clinics, 2) feasibility of having pediatric clinic personnel deliver eHealth Familias Unidas, and 3) acceptability of the intervention from both the participants' and clinic staff's perspective.

To recruit study participants, our study team interfaced with pediatric care staff. Clinic staff let the study team know when (date and time) Hispanic youth between the ages of 12 - 16 (the target age range for the proposed study) and their caregivers were scheduled. During those times, a recruiter/assessor was present to recruit, consent and screen the family. Parent-child dyads were eligible to participate if they self-identified as Hispanic, the youth was between the ages of 12 - 16, both youth and parent were willing to participate, the parent had Internet access, and the family did not have plans of moving from South Florida within the next year.

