### (b) Inclusion criteria

- i) Female and male adolescents of Hispanic immigrant origin, defined by at least one parent born in a Spanish speaking country of the Americas. Parent must understand Spanish given that parent sessions are delivered in this language. In past studies, over 99% of all Hispanic parents understood Spanish.
- ii) Adolescent between the ages of 12 – 16 years
- iii) Adolescent living with an adult primary caregiver who is willing to participate
- iv) Families must have broadband Internet access on a device, including (but not limited to) a smartphone, iPad, tablet, computer at their home or other location (e.g., school, library, etc.)

(c) Exclusion Criteria

- i) Families reporting plans to move out of the South Florida area during the study.
- ii) Families reporting that adolescent has been diagnosed with a developmental delay.

(d) Screening for Eligibility

Clinic staff will let the research team know between a day and two weeks before whether they have Hispanic youth ages 12 - 16 scheduled to come into the clinic and if so at what time. When the potentially eligible family checks in, the family will be moved to a small office space where the assessor and/or facilitator will be. The assessor and/or facilitator will screen parent and youth (separately) by asking parents pre-defined screening questions (i.e. the inclusion criteria). If the participant declines at any moment, verbal consent or assent will be asked for the participant to complete a brief questionnaire.

Additionally, we will do the following:

a) UM/Jackson patients (parents only) will receive a letter (hand delivered, e-mail and/or mail) from their physicians informing them about the study. This letter will inform participants that they will be receiving a call from research study personnel to see if they are interested in participating. Additionally, a phone number will be provided for the potential parent participant to contact research personnel.

b) Research study staff will request permission from each clinic to have access to their scheduling system. On a daily basis, research study personnel will access data on which individuals have a scheduled appointment. No health information will be available to research study staff, only whether there is an appointment scheduled. Study staff will screen these individuals, at the clinic, to see which meet criteria. Study staff will then go to waiting room to recruit those that meet criteria.

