b) Research study staff will request permission from each clinic to have access to their scheduling system. On a daily basis, research study personnel will access data on which individuals have a scheduled appointment. No health information will be available to research study staff, only whether there is an appointment scheduled. Study staff will screen these individuals, at the clinic, to see which meet criteria. Study staff will then go to waiting room to recruit those that meet criteria.

When the potential participating family checks in, clinic staff will briefly introduce the study and ask if the family would like more information. If so, the family will be moved to a small office space or clinical exam room where the assessor and/or facilitator will be at. In the office space or exam room, participants will be asked whether they are interested in learning more about a study to prevent HIV and substance use among Hispanic youth. Parents and adolescents will be screened for eligibility, and if the individual states that he/she meets the criteria and would like to learn more information, the recruitment process will continue. If the family declines, they will be asked to complete a brief questionnaire (detailed below). If the family

would like more information, Familias Unidas facilitators will explain the study in detail to parents and youth and have interested participants sign the informed consent (parents) and informed assent (adolescents). To avoid coercion of the youth by the parent, adolescent and parents will each be in different rooms when they sign consent and assent to ensure that the adolescent has total privacy. In case the adolescent does not want to sign, the family will be told they did not meet one or more of the inclusion/exclusion criteria but the facilitator will not reveal to the parent that the child did not sign (to avoid any consequences to the child). Participants who are not interested in participating in the study will still be asked to provide the following information:

Adolescents: age, gender, lifetime drug use, lifetime sexual activity, grade, nationality and time in the US

Parents: age, gender, income, level of education, nationality and time in the US

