**17) Vulnerable Populations\***

The research involves children under the age of 18. To avoid coercion or undue influence, the adolescents will assent and complete assessments separate from their primary care giver. In case the adolescent does not want to assent, the family will be told they did not meet one or more of the inclusion/exclusion criteria but the facilitator will not reveal to the parent that the child did not assent (to avoid any consequences to the child).

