**29) Consent Process**

**(a) Obtaining Consent**

University of Miami research study personnel will screen families in the clinics that are interested in participating. They will present and read the electronic consent forms to the caregivers who are eligible to participate based on the inclusion and exclusion criteria. The consent form will be an electronic document, and each page will bear the HSRO approval stamp/watermark. If a participant prefers the consent or assent process to be non-electronic, a paper consent or assent form will be provided. After the caregivers understand the study and after all questions have been answered

to their satisfaction, individuals who elect to participate in the study will be asked to sign the consent form. The consent process will last approximately 30 minutes, but it may take caregivers a little less or a little more depending on how clearly they comprehend the study procedures.

If a parent is not available to complete consent, a legal guardian is allowed to provide permission for the adolescent to assent. A legal guardian is a step mother or step father, or another person who has obtained legal rights to the child. During the recruitment screening process, study personnel will determine if the primary caregiver is a legal guardian if they demonstrate the correct paperwork.

Since recruitment will take place at different clinics, it is a possibility that potentially eligible families will visit the clinic when the research team is not present. If the clinic personnel identifies such a family, they will be able to provide them with a flyer about the study and information on how to contact the research team. If the family is interested and contacts the research team, they will be provided with the next date that the research team will be at the clinic so that the family can be informed about the study and conduct the consent, assent and baseline assessment, if the family is interested in being in the study.

(b) Non-English Speaking Subjects

The consent forms will also be available in Spanish. The consent forms have been translated, back-translated and pilot tested for understanding in past pilot studies.

(c) Waiver or Alteration of Consent Process (consent will not be obtained, required information will not be disclosed, or the research involves deception)

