We would like to request information from parents and adolescents that decide not to participate in the study. We are collecting this information because in at least two manuscripts where we report main outcomes for Familias Unidas, reviewers have requested information regarding participants who decide not to engage in the trial. This information will be completely de-identified. We would like to collect this information through the use of a verbal consent and verbal assent. We are requesting permission to only utilize a verbal consent and assent (not signed) because it is unlikely that participants who do not want to participate in the study will answer these questions if they have to identify themselves by signing a consent or assent form.

(d) Subjects who are not yet adults (infants, children, teenagers)

Adolescents, ages 12-16, will go through a similar process as their parents. Their age is confirmed with the pediatric clinic administrator, nurses, and/or physician. After the parent has consented, the facilitators will present the assent forms to the adolescent. This will occur in a different room without the caregivers present to prevent the adolescents from being coerced to participate. Only the adolescent present for the clinic appointment will complete the assent form. The assent process will last approximately 30 minutes, but it may take the adolescent a little more or a little less depending on how clear they comprehend study procedures.

(e) Cognitively Impaired Adults  
Not applicable.

(f) Adults Unable to Consent  
Not applicable.

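### Because assent is sought only after the parent has been screened and has consented, telling the family it failed a criterion can let the parent infer the child's refusal, and the message is not true on the current criteria list

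*Combined protocol and SAP*

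**What the plan says.** Section 7(a), Study-Wide Recruitment Methods, sets the rule for an adolescent who will not sign: "the family will be told they did not meet one or more of the inclusion/exclusion criteria", and "the facilitator will not reveal to the parent that the child did not sign (to avoid any consequences to the child"). Section 17, Vulnerable Populations, repeats it: "the facilitator will not reveal to the parent that the child did not assent (to avoid any consequences to the child").

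The steps that come before this message are described in four places.

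- Section 5(d), Screening for Eligibility: "The assessor and/or facilitator will screen parent and youth (separately) by asking parents pre-defined screening questions (i.e. the inclusion criteria").
- Section 7(a): parents and adolescents are both screened, and recruitment goes on only when the person says the criteria are met and wants to hear more.
- Section 29(a), on who is given the consent form: "They will present and read the electronic consent forms to the caregivers who are eligible to participate based on the inclusion and exclusion criteria".
- Section 29(d): "After the parent has consented, the facilitators will present the assent forms to the adolescent". This takes place in a different room from the caregiver.

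Sections 5(b) and 5(c) list the criteria. On its natural reading, the only willingness criterion concerns the caregiver. The feasibility pilot described in section 4(b) was different. There, a dyad was eligible only if, among other things, "both youth and parent were willing to participate".

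**The concern.** The message is meant to be a cover story. It works only if the parent can believe that some criterion was failed. If the parent has already passed every criterion and signed, the natural explanation left is the child's private decision.

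The protocol itself says what is at stake: protecting a minor from consequences at home and from pressure to take part. The study concerns drug use and sexual behaviour, so a refusal may itself suggest something to a parent. A safeguard that can disclose the refusal does not do the job it was written for. Separately, staff are directed to give families a reason that the protocol's own criteria do not support.

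**Working it through.** No arithmetic bears on this point. The check is to put the steps in order and ask which criteria could still fail at the last one.

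**Order of events**

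1. Parent and youth are screened separately, and the parent is asked the inclusion criteria (5(d), 7(a)).
2. The process continues only if the criteria are stated to be met (7(a)).
3. The consent form is presented to caregivers who are eligible on both inclusion and exclusion criteria (29(a)).
4. The parent consents.
5. The adolescent is offered assent privately (29(d)).
6. If the adolescent declines, the family is told that a criterion was not met (7(a), 17).

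The only step described between the parent's consent and the message is the adolescent's assent decision.

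**Could a criterion plausibly have failed at step 6?** The list has four inclusion items and two exclusion items. The first inclusion item holds two requirements, which makes seven.

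| Requirement | Would the caregiver normally know it? |
|---|---|
| A parent born in a Spanish-speaking country of the Americas | Yes |
| Parent understands Spanish | Yes |
| Adolescent aged 12 to 16 | Yes |
| Adolescent lives with a caregiver willing to take part | Yes |
| Broadband access on some device | Yes |
| No plan to leave South Florida | Yes; rests on the family's own report |
| No diagnosed developmental delay | Yes; rests on the family's own report |

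No requirement depends on something only the youth knows. A parent who reached step 4 has reason to believe that all seven were met.

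**Is the message true?** Assent is not on the list, and the youth's willingness is not stated separately. A family whose youth declines at step 5 has met every listed criterion, so the message is not true on that list. Under the pilot's criteria it would have been true.

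**The non-participant questionnaire.** Section 5(d) provides for a short questionnaire when someone declines at any point. Section 7(a) seeks the same data from people who refuse after screening. Neither section says what happens in a family that has been given the ineligibility message. Nothing directs staff to put the questions to a parent who consented, but nothing excludes it, and being asked could also signal a refusal.

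**The case against.** The strongest reply is that youth are screened too, separately, and the parent does not hear their answers. Section 29(d) has clinic staff confirm the youth's age, and section 29(a) has study staff check guardianship paperwork. A parent could suppose that one of these checks failed. The text also says who receives the consent form, not that the parent is told an eligibility result, and the consent forms themselves are not available to read. Some reluctant youths will drop out earlier, at the point where the individual must want more information. No procedure that starts after parental consent can hide a refusal completely.

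Part of this stands. The message *can* reveal the refusal; it does not follow that it always will. But the youth screening gives only weak cover, because it also comes before consent and none of the criteria turns on facts private to the youth.

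A reader might also infer three stronger things that the documents do not support.

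- *Refusals are logged as ineligibility.* Sections 7(a) and 17 govern only what the family is told. Section 7(a) separately recognises people who refuse after screening.
- *Youths pressed into assenting will under-report the primary outcomes.* No passage shows this. Assessments are completed apart from the caregiver, self-report is electronic, and a Certificate of Confidentiality is in place. STI incidence is laboratory-tested. Assent precedes randomisation, so pressure at entry would apply to both arms.
- *The number of families affected can be derived from the screening target.* Section 24 gives about 2,500 subjects screened and 912 enrolled. The remainder, 2,500 − 912 = 1,588, mixes ineligible families, parental refusals and early declines, and no youth-refusal share is given.

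**Conclusion.** The point holds as a gap in participant protection. As sequenced, the cover message can let a parent infer the refusal it is meant to hide, and it is not true on the current criteria list. The conclusion rests on two readings: that section 29(d) fixes the order of consent and assent, and that the willingness criterion in section 5(b) refers to the caregiver. Both are the plain sense of the text.

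The families concerned are those in which the parent consents and the youth then declines. Their number cannot be stated from the documents. Alpha, power, sample size and the planned analyses are unaffected. The case for changing the text is that the protocol's stated purpose is not met and the remedy is cheap.

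**What to change.** Amend sections 5(b), 5(d), 7(a), 17 and 29(d) together so that they describe one sequence.

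1. Add the adolescent's willingness to take part to the criteria in 5(b), as in the feasibility pilot.
2. Ask about it privately, in the separate youth screening that already exists under 5(d).
3. Give the parent no eligibility result and no consent form until that screening is complete. Formal assent can stay after parental consent, as in 29(d).
4. State in 5(d) and 7(a) that the non-participant questionnaire is not put to a parent who was given the ineligibility message.

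The timing in step 3 is essential. Adding the criterion alone would make the message true but would leave the youth's willingness as the only criterion that could have failed after the parent signed. With the revised order, a youth who declines at screening does so before the parent has been treated as eligible.

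The cost is protocol wording and IRB approval of the revised order, with no added staff. The only added question is one on willingness, asked in a screening that already takes place. Two limits remain. A parent may still suspect a refusal, though with less to go on. A youth who agrees at screening but changes their mind at formal assent is still not fully protected, and the protocol should acknowledge this.

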This collected information from non-participants will not contain any names, therefore, it will be de-identified. We will attempt to collect this information from participants who say no at initial contact and from participants who go through the screening and then refuse to participate. To collect this information, we will request verbal consent and assent. We are requesting permission to only utilize a verbal consent and assent because it is unlikely that participants who do not wish to participate in the study will answer these questions if they have to identify themselves by signing a consent form.

For participating families, once the family completes the consent/assent, they complete the baseline assessment. Once the baseline assessment is complete, adolescent will take an STI test, and the family is blindly randomized to one of the two study conditions, they, the primary caregiver and adolescent, will be compensated for their time.

Families that are interested in participating in the study, but do not have time to complete consent/assent and baseline assessment in the clinic will be offered the option to be visited at home. If the family agrees, a research team member will visit the family during an arranged time to complete the consent/assent, baseline assessment and urine test with the adolescent.

Total time to recruit, including baseline assessment, randomization and compensation, will be approximately 45 minutes, but it may vary from family to family depending on whether or not the family needs more or less time to comprehend the study procedures. At each of the five assessment time points, baseline, 6, 12, 24, 36 months, the parent will be compensated, \$40, \$45, \$50, \$55 and \$60, respectively. At each of the assessment time points, baseline, 6, 12, 24, 36

months, the adolescent will be compensated with \$20 cash for completing both the survey and the STI test.

(b) **Materials**

Posters will be hung at each of the primary care offices. The poster will be an enlarged version of the flyer.

8) **Study Timelines**

(a) The duration of an individual subject's participation in the study

4 years

(b) The duration anticipated to enroll all study subjects

2 years

(c) The estimated date for the investigators to complete this study

February 2022

9) **Study Endpoints**

(a) Study endpoints

i) Primary:

- Frequency of (past 90-day) drug use in Hispanic adolescents over time.

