- Frequency of (past 90-day) unprotected sex in Hispanic adolescents over time.
- STI incidence (specifically, the incidence of gonorrhea and chlamydia).

ii) Secondary:

- Improvements in family functioning over time (e.g. parent-adolescent communication, parental monitoring of peers).
- Frequency of unprotected sex will be partially mediated by improvements in family functioning over time.
- Reduction of STI incidence will be partially mediated by improvements in family functioning and decreases in unprotected sex over time.

(b) Safety endpoints

Not applicable.

10) **Procedures Involved**

(a) Study Design

This study tests the effectiveness of eHealth Familias Unidas Primary Care in preventing drug use, unprotected sexual behavior, and STIs in a universal sample of Hispanic youth, this study will use a randomized trial design with two levels of intervention (eHealth Familias Unidas Primary Care and prevention as usual) as the between subjects factor with five repeated measures assessments at baseline, 6, 12, 24, and 36 months post baseline as the within subject factor.

Once both primary care giver and adolescent have completed the consent/assent, they will complete the baseline assessment electronically. Once the baseline assessment is complete, they will be randomized to one of the two conditions: eHealth Familias Unidas Primary Care (experimental prevention as usual (control) Condition. Please see attached for consent/assent forms (in English and Spanish). All consent forms will be completed electronically. All confidential study participant information will be stored electronically in secure University of Miami systems.

i) eHealth Familias Unidas Primary Care

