the web server safe from intrusion. Additionally, a Secure Socket Layer Encryption certificate will be issued to help prevent Internet fraud. The implementation of SSLs (i.e., cryptographic protocols) aims to enhance security over the Internet. IT will conduct stringent testing of web applications prior to the implementation of eHealth Familias Unidas Primary Care to prevent any exploits from occurring and to ensure the confidentiality of participants.

ii) Control Condition

Participants randomized to the control condition continue prevention as usual. These participants will not be receiving any services from our staff. These participants will only be asked to complete a survey at each of the 5 time points: when they first enroll, and at 6, 12, 24, and 36 months. The adolescent will also be asked to provide a sample for an STI test during each of these time points.

(b) Assessments

After the intervention is complete, assessors will call the families to return to complete follow up assessments. The follow up assessments will occur on the University of Miami Miller School of Medicine Campus, at the clinic sites or at the homes of the participants. The follow up assessments collect the same data as the baseline assessment. All measures will be self-report and completed using survey software provided by the study team

(c) Data Collection

Demographics. A demographics form developed by the creators of Familias Unidas will be administered to caregivers and youth in order to collect information on contact information, age, date/place of birth, number of years residing in the U.S., parents' marital status, and family income.

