In addition to the self-report measures described above, we will measure gonorrhea and chlamydia by a real-time PCR assay for the direct, qualitative detection of the plasmid DNA of *Chlamydia trachomatis* and the genomic DNA of *Neisseria gonorrhoea* which is currently being used in clinical practice and clinical trials at our institution. This assay has shown high sensitivity and specificity for the detection of both organisms in asymptomatic and symptomatic patients. Youth who test positive for an STI will be referred to treatment. Youth will also be encouraged to refer sex partners for treatment. The county health department will be notified of reportable STIs. For analyses, sexually transmitted infection incidence will be defined as a positive laboratory test result for a new chlamydia or gonorrhea infection at any of the five assessment time points. Previous studies with ethnic minority youth have demonstrated feasibility and a high acceptance rate with respect to the collection of biological markers for determining STI incidence.

We would also like to collect data from clinic facilitators, clinic leaders, and physicians to assess organizational level factors and attitudes towards evidence-based interventions. To do this, we will use the below measures:

*Attitudes Towards Evidence-Based Practice Scale (EBP; facilitator; 15 items): this measure will be administered to facilitators to assess their views on evidence-based practices.*

*Multifactor Leadership Questionnaire (clinic leaders/physician, 21 items): this measure will be administered to clinic leaders/physicians to assess transformational and transactional leadership behavior.*

*Implementation Leadership Scale (ILS; Clinic leaders/physicians, 11 items): this measure assesses the degree to which organizational leaders support their staff in the implementation of evidence-based interventions*

*Implementation Climate Scale (clinic leaders/physician, 18 items): assesses the level of a strategic organizational climate within an organization.*

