This hypothesis will be analyzed using a univariate logistic regression for the binary outcome, new diagnoses of STIs (Yes/No). STI incidence will be defined as a positive laboratory test result for a new chlamydia or gonorrhea infection at any of the four follow up assessment timepoints. In the analysis for this hypothesis, condition will predict STI diagnosis. The test of the hypothesis will be based on a Wald test comparing the intervention regression coefficient to its standard error. Additionally, the time of STI diagnosis will be included as a covariate in the logistic regression to test the robustness of the intervention's effect.

**Power.** According to CDC national statistics, the annual STI incidence rate is 3.16% for Hispanic adolescents aged 15 to 19. Thus, we expect the 3-year STI incidence rate in the control group to be approximately 9.2%. Using a one-sided Z test with pooled variance to test the difference between two independent proportions (assuming the same 5% attrition rate at each assessment timepoint), the study has over 80% power to detect a difference of 6.1% in STI incidence between the two conditions. This difference in proportions translates to an effect size of Cohen's  $h = 0.26$ , considered a small ( $h = 0.2$ ) to medium ( $h = 0.5$ ) effect size, according to Cohen (1988).

**H2a:** *Intervention effects on frequency of drug use will be partially mediated by improvements in family functioning over time.*

To test for mediation, we will use the "product of coefficients" test described by MacKinnon and colleagues, which is based on the distribution of the indirect effect of the intervention through the mediator (Cohen, 1988). This procedure tests whether the product of the coefficients from the intervention to the mediator (a) and from the mediator to the outcome (b) is significantly different from zero. Specifically, we will estimate paths between intervention and family functioning (a), and between family functioning and drug use (b). Because we have five time points, our first mediation analyses will fit bivariate growth curves for both family functioning and drug use and examine the role of the (latent) slope of family functioning on the slope of

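### The STI endpoint has two event windows: section 10(c) counts five time points, including the pre-randomization baseline test, while the H1c analysis counts only the four follow-ups

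*Combined protocol and SAP*

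**What the plan says.** STI incidence (gonorrhea and chlamydia) is one of three primary endpoints in section 9(a). Its event rule is written twice.

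- Section 10(c), Data Collection, in a sentence that says it applies to the analyses: "a positive laboratory test result for a new chlamydia or gonorrhea infection at any of the five assessment time points".
- Section 12(a), Data Analysis Plan and Power Analysis, under H1c: "new chlamydia or gonorrhea infection at any of the four follow up assessment timepoints".

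Three other places fix what the fifth time point is. Section 10(a) describes "five repeated measures assessments at baseline, 6, 12, 24, and 36 months post baseline". Section 10(a)(ii), on the control condition, lists the same five occasions and adds: "The adolescent will also be asked to provide a sample for an STI test during each of these time points". Section 7(a) gives the order of events at enrolment: "Once the baseline assessment is complete, adolescent will take an STI test, and the family is blindly randomized".

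The H1c power paragraph starts from an annual rate of 3.16% and says "we expect the 3-year STI incidence rate in the control group to be approximately 9.2"%.

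**The concern.** One primary endpoint has two derivation rules that differ on whether a result obtained before randomization can be an outcome event. The documents do not say which section prevails. A programmer who derives the variable from the section that defines the measure would include the baseline test; one who works from the H1c text would not.

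Under the section 10(c) rule, infections already present at enrolment are events in both arms. Randomization makes them about equally frequent in the two arms, and the intervention cannot change them. H1c is tested by logistic regression, and adding a similar number of events to each arm moves the odds ratio toward 1. Few events are expected, so a handful is enough to matter. Leaving both rules in place would also allow a choice between them after outcome data are seen.

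**Working it through.** **1. Do the two sentences really differ?** The five assessments are baseline, 6, 12, 24 and 36 months (section 10(a)); the four follow-ups are the last four. The difference is exactly the baseline test, which precedes randomization (section 7(a)). Both sentences require a new infection, but neither defines the term. No study test comes before baseline, so the study's own results cannot show whether a baseline positive is new. The word therefore does not bring the two rules together.

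**2. Which rule does the power calculation use?** Compounding the stated annual rate over three years gives 1 − (1 − 0.0316)³ = 0.0918, which is the plan's 9.2%. There is no baseline term, so the figure fits the four-follow-up rule.

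**3. The plan's power figure.** Inputs from section 12(a): control 9.2%; difference 6.1 points, so intervention 9.2 − 6.1 = 3.1%; 185 per arm at the final assessment (228 × 0.95⁴ = 185.7); one-sided pooled-variance Z test. Alpha is not stated for H1c, so one-sided 5% is assumed.

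- Pooled proportion: (0.092 + 0.031)/2 = 0.0615
- SE under the null: √(2 × 0.0615 × 0.9385/185) = 0.02498
- SE under the alternative: √((0.092 × 0.908 + 0.031 × 0.969)/185) = 0.02478
- Power: Φ((0.061 − 1.645 × 0.02498)/0.02478) = Φ(0.80) = 78.9%

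The plan says over 80%. The gap is about one point; 191 per arm would reach 80%. Cohen's h is 0.262, against the stated 0.26.

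**4. Effect on the odds ratio.** Expected events at 185 per arm are 185 × 0.092 = 17.0 (control) and 185 × 0.031 = 5.7 (intervention). Suppose section 10(c) adds k adolescents per arm who are positive at baseline and would not otherwise be events:

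| k per arm | Events, control v intervention | Odds ratio |
|---|---|---|
| 0 | 17.0 v 5.7 | 0.316 |
| 1 | 18.0 v 6.7 | 0.350 |
| 2 | 19.0 v 7.7 | 0.381 |
| 5 | 22.0 v 10.7 | 0.456 |

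**5. Illustration of power.** The documents give no baseline prevalence, so b is an assumption, equal in both arms. If baseline and later infection are independent, the event probability becomes q = 1 − (1 − b)(1 − p). Test, alpha and 185 per arm are as in step 3.

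| Assumed b | q, control v intervention | Difference (points) | Odds ratio | Power |
|---|---|---|---|---|
| 0 | 9.2% v 3.1% | 6.1 | 0.316 | 78.9% |
| 0.25% | 9.4% v 3.3% | 6.1 | 0.332 | 77.5% |
| 0.5% | 9.7% v 3.6% | 6.1 | 0.348 | 76.1% |
| 1% | 10.1% v 4.1% | 6.0 | 0.377 | 73.3% |
| 2% | 11.0% v 5.0% | 6.0 | 0.429 | 68.2% |
| 3% | 11.9% v 6.0% | 5.9 | 0.472 | 63.6% |

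If half of the baseline positives would also test positive later, only half are extra events (q = p + 0.5b) and the loss is smaller: power 76.3% and odds ratio 0.348 at b = 1%; 71.4% and 0.402 at b = 3%.

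**The case against.** The best reply is that the analysis plan is already right. Section 12(a) names the model, the test and the event window for H1c, whereas section 10(c) describes measurement. Run as section 12(a) says, H1c is sound. This stands, and it limits the harm to the case where section 10(c) is taken literally. It does not remove the conflict, because the section 10(c) sentence presents itself as the analysis definition and no order of precedence is given.

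A second reply is that incidence and new already shut out a first-ever positive test. That reading is possible and makes the harm less likely. But the term is undefined in both places, and on that reading naming five time points would still be wrong.

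A third is that the power series rests on assumptions. This also stands. Prevalence, alpha and overlap are not in the documents, and nothing in them supports 2–3% in a universal sample aged 12–16. The level also depends on the denominator: with all 228 per arm, the same formula gives 85.9% with no baseline events and 80.9% at 1% prevalence. That is an upper bound, because dropouts have incomplete follow-up. The illustration also uses the Z test of the power paragraph, not the logistic Wald test planned for H1c. Direction is certain; size is not.

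Lastly, changing the window leaves new undefined for an adolescent positive at baseline and again at 6 months. That is correct, and the gap exists under the H1c text too.

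**Conclusion.** The concern holds. The plan gives two incompatible event windows for a primary endpoint, and the one in section 10(c) is wrong as written: it admits a pre-randomization result and does not match the basis of the 9.2% control rate. The error matters only if that wording drives the derivation. The odds ratio would then be biased toward 1, by an amount set by the unknown baseline prevalence, while the risk difference would barely move. The odds ratios in step 4 need only the plan's rates, 185 per arm, and k extra events in each arm. The power figures are an illustration under assumed prevalence and alpha. The point should be fixed; it does not undermine the H1c analysis as section 12(a) specifies it.

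**What to change.** In section 10(c), replace the reference to five assessment time points with the four follow-up assessment time points (6, 12, 24 and 36 months), so that it agrees with H1c in section 12(a). Report baseline positives by arm as baseline prevalence, not as outcome events. If new is to be defined for adolescents who are positive at baseline, base the rule only on test results already scheduled, and put the same rule in both sections. Make the change before outcome data are examined.

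Cost: one line of protocol text and one row in the baseline table. Urine is already collected at every time point, so there is no new data collection, and the sample size does not change.
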